**Table 1. Study Schedule of Assessment**

Visit Identifier	Screen	On-Treatment Period (28-day Cycle)												Notes			
		Cycle 1				Cycle 2-3				≥Cycle 4				EOT	FU visits		LTFU
Cycle Day	≤28d	D1	D4	D8	D15	D22	D1	D8	D15	D22	D1	D15	7d	28d	90d	Q12W	
 
Day relative to start of study intervention (Day 1).
 

Visit Window		(±1d)	(±2d)	(±2d)	(±2d)	(±2d)	(±2d)	(±2d)	(±2d)	(±2d)	(±2d)	(±2d)	(±2d post-last TX)	(28-35d post-last TX)	(+7 post-last TX)	(±14d post 90d FU)	
 
After 1 year of study intervention, cycle visit date windows are ±7d.
 

HIV status	X																
 
For participants with known history of HIV: CD4 count and viral load
 

Hepatitis B/C panel	X																
 
Monitor participants for HBV reactivation throughout the study, if applicable.
 
See Appendix 2, Appendix 10, and REVIMID SmPC.
 

Pregnancy test (WOCBP only)	X	X		X	X	X	X	X*		X	X*		X				
 
Pregnancy test will be done weekly at C1; and monthly at C2 and beyond.
 
*: WOCBP participants with irregular cycles should have the test done every 2 weeks.
 
See Section 8.3.5 for additional information.
 

Contraception check	X	X					X			X			X	X			
 
Only required for WOCBP and men with WOCBP partner.
 
See Section 4.2.3 and Appendix 4 for additional information.
 

FSH	X																
 
For confirmation of postmenopausal status.
 

Hematology	X	X	X	X	X	X	X	X	X	X	X	X	X				
 
May be collected up to 72 hours prior to dosing visit date.
 
See Appendix 2.
 

PFIZER CONFIDENTIAL

CT02-GSOP Oncology Clinical Protocol Template (01 April 2022)

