**Table 1. Study Schedule of Assessment**

Visit Identifier Abbreviations used in this table may be found in Appendix 16	Screen	On-Treatment Period (28-day Cycle)												Notes					
		Cycle 1					Cycle 2-3				≥Cycle 4			EOT	FU visits				
Cycle Day	≤28d	D1	D4	D8	D15	D22	D1	D8	D15	D22	D1	D15	7d	28d	90d	Q12W	
 
All screening should be done ≤28 days before the first dose, unless noted otherwise.
 
		
Visit Window		(±1d)	(±2d)	(±2d)	(±2d)	(±2d)	(±2d)	(±2d)	(±2d)	(±2d)	(±2d)	(±2d)	(±2d post-last TX)	(28-35d post-last TX)	(+7 post-last TX)	(±14d post 90d FU)	
 
Day relative to start of study intervention (Day 1).
 
After 1 year of study intervention, cycle visit date windows are ±7d.
 
		
ADA/NAb for PF-07901801 (PB)		X					X				X		X	See Notes		
 
C1D1, C2D1, C3D1, C4D1 and C5D1: pre-dose.
 
Starting C7 up to C13, collect pre-dose only every 3rd cycle (ie, C7D1, C10D1, C13D1) and then every 6th cycle thereafter (C19D1, C25D1, etc.).
 
FU visits and LTFU: Participants with an unresolved AE at the end of study treatment considered possibly related to ADA formation may be asked to return to the clinic for ADA blood sampling at approximately 3-month intervals (if feasible given the underlying disease) until the AE or its sequelae resolve or stabilize at a level acceptable to the investigator and sponsor up to a maximum of 9 months from the last study treatment.
 
			

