### 2.3.1. Risk Assessment

Phase 2 of the study will not be initiated per business decision made by Pfizer (protocol amendment 2).

Potential Risk of Clinical Significance	Summary of Data/Rationale for Risk*	Mitigation Strategy
PF-07901801+tafasitamab+ lenalidomide		
Thrombocytopenia	
G3-4 thrombocytopenia was observed in 17.3% of the patients treated with tafasitamab and lenalidomide.
 
Treatment-related G3-4 thrombocytopenia (5%) has been reported with PF-07901801 in the ongoing Phase 1 Study C4971001. The combination may increase the risk of G3-4 thrombocytopenia.
	
Participants must have adequate hematological functions (including platelet counts with no transfusions for at least 2 weeks prior to C1D1) to be eligible to participate in this study. Participants will have weekly hematology blood tests for the first 3 cycles and thereafter every two weeks (or more frequently if clinically indicated).
 
Platelet transfusion is allowed to manage severe thrombocytopenia, to prevent and minimize bleeding according to institutional guidelines (see Section 6.9.4).
 
Dose interruption and dose modification are described in Section 6.6.1.

Neutropenia	
G3-4 neutropenia was reported in 48.1% of the patients treated with tafasitamab and lenalidomide.
 
Treatment related, G3-4 neutropenia (9%) has been reported with PF-07901801 in the ongoing Phase 1 Study C4971001. The combination may increase the risk of G3-4 neutropenia.
	
Participants must have adequate hematological functions (including neutrophil counts, with no growth factor for at least 2 weeks prior to C1D1) to be eligible to participate in this study. Participants will have weekly hematology blood tests for the first 3 cycles and thereafter every two weeks (or more frequently if clinically indicated).
 
Prophylactic use of granulocyte-colony stimulating factors is not permitted during the DLT period of Phase 1b but can be used in later cycles and in Phase 2 of the study. G-CSF may be used to treat treatment emergent neutropenia as per institutional guidelines.
 
Any symptoms or signs of developing infection should be anticipated, evaluated and treated.
 
Dose interruption and dose modification are described in Section 6.6.1.

Potential Risk of Clinical Significance	Summary of Data/Rationale for Risk*	Mitigation Strategy
PF-07901801+tafasitamab+ lenalidomide		

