#### **Disease Characteristics:**

2. Histologically confirmed, measurable relapsed and/or refractory DLBCL NOS, T cell/histiocyte rich large B-cell lymphoma; or EBV positive DLBCL, according to the 5th edition of the WHO Classification of Lymphoid Neoplasms. Further, follicular lymphoma grade 3b, or composite lymphoma with a DLBCL component with a subsequent DLBCL relapse.
  - Participants with evidence of histological transformation to DLBCL from an earlier diagnosis of low grade lymphoma (ie, an indolent pathology such as follicular lymphoma, marginal zone lymphoma, chronic lymphocytic leukemia) are eligible if relapsed or refractory to at least one line of therapy for DLBCL (for primary refractory, see exclusion criterion #2 below).
3. Participant characteristics:
  - Not a candidate per investigator or unwilling to undergo high dose chemotherapy and subsequent autologous stem cell transplant or unable to receive approved CAR-T therapy (eg, logistical limitations).

- Measurable disease: at least 1 site of measurable, PET-avid disease per Lugano 2014 classification (index lesion: >1.5 cm in the longest diameter for nodal, >1.0 cm in the longest diameter for extranodal disease).

4. Prior systemic treatment regimen:

- Must include an anti-CD20 containing regimen:
  - Phase 1b: at least 1 prior line of systemic therapy.
  - Phase 2: at least 1 but no more than 2 prior lines of systemic therapy.

For both phases: induction, ASCT and consolidation will be considered one line of therapy; bridging therapy prior to CAR-T and CAR-T treatment will be considered together as one line of therapy.

- If exposed to prior CD19-targeting CAR-T therapy:
  - Last CAR-T infusion must have been completed >90 days prior to C1D1.
  - Provide CD19 expression test at Screening as per local lab, if available, and must provide a tissue sample for retrospective central testing (see also inclusion criterion #8 and [Section 8.7.8](#)). CD19 positivity is not required.

5. Adequate organ function:

- Hematology (with no transfusion or growth factor support for at least 2 weeks prior to C1D1):
  - ANC  $\geq$ 1,000/ $\mu$ L.
  - Platelet count  $\geq$ 90,000/ $\mu$ L.
  - Hemoglobin  $\geq$ 8 g/dL.
- Hepatic function:
  - T bili  $\leq$ 2.0  $\times$  ULN. Participants with documented Gilbert's syndrome are eligible for this study providing the direct bilirubin is  $\leq$ ULN.
  - ALT and AST  $\leq$ 2.5  $\times$  ULN.
- Renal function:

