#### **6.6.2. Re-Treatment After Toxicity**

Re-treatment following treatment interruption for treatment-related toxicity or at the start of any new cycle may not occur until all of the following parameters have been met:

- ANC  $\geq 1000/\mu L$ ;
- Platelet count  $\geq 50000/\mu L$ ;
- Hemoglobin is  $\geq 8 \text{ g/dL}$ ;
- Recovery of treatment-related non-laboratory toxicities to baseline or  $\leq G1$  severity.
- Recovery of treatment-related non-hematologic laboratory toxicities to baseline or  $\leq G2$  severity.

If a treatment interruption results from worsening of hematologic or biochemical parameters, the frequency of relevant blood tests is to be increased as clinically indicated.

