#### **6.9.4. Hematopoietic Growth Factors and Blood Product Transfusions**

Participants must have adequate hematological function with no transfusion or colony stimulating factor or erythropoiesis-stimulating agent for at least 2 weeks prior to C1D1 to be eligible to participate in this study.

Primary prophylactic use of colony stimulating factors or erythropoiesis-stimulating agents is not permitted during the first 28 days of Phase 1b C1, ie, DLT observation period.

If hematopoietic growth factors or blood product transfusions are required to manage an AE that did not meet DLT criteria, the DLR team may determine if the AE is a DLT or that the participant is not DLT-evaluable (and may need to be replaced).

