#### **8.3.4. Clinical Safety Laboratory Assessments**

See [Appendix 2](#) for the list of clinical safety laboratory tests to be performed and the [SoA](#) for the timing and frequency. All protocol-required laboratory assessments, as defined in [Appendix 2](#), must be conducted in accordance with the Laboratory Manual and the [SoA](#). Unscheduled clinical laboratory measurements may be obtained at any time during the study to assess any perceived safety issues and results recorded in the CRF.

The investigator must review the laboratory report prior to the infusions, document this review, and record any clinically significant changes occurring during the study in the AE section of the CRF. Clinically significant abnormal laboratory test findings are those that are not associated with the underlying disease, unless judged by the investigator to be more severe than expected for the participant's condition.

All laboratory tests with values considered clinically significant and abnormal during participation in the study or within 28 calendar days after the last administration of PF-07901801 and/or lenalidomide or 90 days after the last administration of tafasitamab should be repeated until the values return to normal or baseline or are no longer considered clinically significant by the investigator or study medical monitor.

If such values do not return to normal/baseline within a period of time judged reasonable by the investigator, the etiology should be identified and the sponsor notified.

See [Appendix 6](#) for suggested actions and follow-up assessments in the event of potential DILI.

See [Appendix 7](#) for instructions for laboratory testing to monitor kidney function and reporting laboratory test abnormalities.

Screening laboratories may be used as pre-dose baseline if they are within 3 days of C1D1, and therefore there is no need to repeat clinical laboratory assessments on C1D1 in this case. If laboratory values are not within eligibility, blood test may be repeated once.

All safety laboratory results must be available prior to dosing to determine if dose modifications are necessary, may be drawn up to 72 hours prior to dosing visit date.

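### Criterion 5 counts the transfusion and growth-factor washout from C1D1, not from the qualifying sample, and the protocol does not say whether the fresh pre-dose count must meet the eligibility limits

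*Protocol*

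**What the plan says.** Protocol Section 5.1, criterion 5, opens its count limits with "Hematology (with no transfusion or growth factor support for at least 2 weeks prior to C1D1" and then requires ANC of at least 1,000/µL, platelets of at least 90,000/µL and hemoglobin of at least 8 g/dL. The anchor is the same in Section 6.9.4, "Participants must have adequate hematological function with no transfusion or colony stimulating factor or erythropoiesis-stimulating agent for at least 2 weeks prior to C1D1", and in the thrombocytopenia row of Section 2.3.1, "Participants must have adequate hematological functions (including platelet counts with no transfusions for at least 2 weeks prior to C1D1".

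The age of the qualifying sample is set elsewhere. The Schedule of Activities (Table 1) says "All screening should be done ≤28 days before the first dose, unless noted otherwise". Section 8.1 also lets routine blood counts taken before consent serve as screening results if they fall in that window.

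A later count exists. Table 1 marks hematology at both Screening and C1D1, with the note "May be collected up to 72 hours prior to dosing visit date". Section 8.3.4 says "Screening laboratories may be used as pre-dose baseline if they are within 3 days of C1D1", and the next sentence reads "If laboratory values are not within eligibility, blood test may be repeated once". The same section requires results to be available before dosing so that dose modifications can be decided, and requires the investigator to review them before the infusions.

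Section 6.6.2 sets a further set of limits: "Re-treatment following treatment interruption for treatment-related toxicity or at the start of any new cycle may not occur until" ANC is at least 1,000/µL, platelets at least 50,000/µL and hemoglobin at least 8 g/dL.

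**The concern.** The washout and the count limits exist to show that the participant's marrow meets the limits unaided. That works only if the count being judged was drawn in the unsupported period. Here the washout is tied to C1D1, the count is tied to Screening, and no passage links the two.

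Two things are at stake. Section 2.3.1 relies on adequate counts without recent support as the first mitigation for thrombocytopenia, neutropenia and anemia. Also, the hematologic DLT limbs in Section 4.3.4.1 use absolute grades or counts, and the dose decision rests on 2 to 4 participants per cohort. Someone who starts treatment with low unsupported counts could reach those grades more easily.

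**Working it through.** The plan gives no figure for this point, so the check is calendar arithmetic, a reading of the passages that could close the gap, and a look at the decision table.

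**1. Calendar.** The screening window is 28 days (Table 1) and the washout is 14 days before C1D1 (criterion 5). Days on which a qualifying sample can precede the washout: 28 − 14 = 14, that is Day -28 to Day -15, or 14/28 = half the window. Example: transfusion on Day -20, qualifying count on Day -19, no support afterwards. The last support is 20 days before C1D1 (≥14, passes). The sample is 19 days old (≤28, passes). The sample was drawn 1 day after support, and no rule addresses that interval.

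**2. Could another passage catch a low unsupported count at C1D1?**

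| Passage | Reaches the pre-C1D1 count? | Applies the criterion 5 limits? |
|---|---|---|
| Table 1 and Section 8.3.4, fresh count within 3 days | Yes | Not stated; uses given are baseline and dose modification |
| Section 8.3.4, single repeat when values fall outside eligibility | Unclear; it follows the C1D1 sentence but does not name the sample | Only if it refers to that sample |
| Section 6.6.1, Table 6 | No; it covers treatment-related toxicity, which cannot exist before the first dose | No |
| Section 6.6.2 | Unclear; headed re-treatment, but mentions the start of any new cycle | ANC and hemoglobin the same; platelets 50,000 against 90,000/µL |

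If Section 6.6.2 covers Cycle 1, the open range is platelets from 50,000 up to 90,000/µL. If it does not, all three counts are open. By contrast, Section 8.3.5 does require re-confirmation for pregnancy: a second negative test at baseline, before treatment.

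**3. Sensitivity of the dose decision.** From Protocol Table 12, one additional DLT changes 0/2 from E to D (1/2), 0/3 from E to S (1/3), 0/4 from E to S (1/4) and 1/3 from S to D (2/3). Rebuilding mTPI-2 with a Beta(1,1) prior and a 0.95 exclusion cut-off (both assumed, as the documents do not state them) reproduces 89 of the 90 cells in rows 0 to 6. The exception, 6 of 11, is not used here.

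**4. Illustration on assumed inputs only.** Let f be the share of participants qualified on a supported count, m their DLT rate and p the rate in the others. The mixed rate is q = (1 − f)p + fm, so the rise is f(m − p). Take f = 0.05 to 0.20, m = 0.3 to 0.5, and p = 0.10 or 0.20.

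- Smallest rise: 0.05 × (0.30 − 0.20) = 0.005. Largest: 0.20 × (0.50 − 0.10) = 0.08.
- n = 3 escalates only on 0 DLTs, so P(not escalating) = 1 − (1 − q)³. For p = 0.10 it goes from 0.271 to between 0.295 and 0.449. For p = 0.20 it goes from 0.488 to between 0.498 and 0.595.
- n = 6 escalates on 0 or 1 DLT, so P = 1 − (1 − q)⁶ − 6q(1 − q)⁵. For p = 0.10 it goes from 0.114 to between 0.134 and 0.296. For p = 0.20 it goes from 0.345 to between 0.357 and 0.490.

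The documents give no value for f, m or p. The ranges show only that the effect runs from negligible to material.

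**The case against.** The strongest reply is that nobody is dosed on a 28-day-old count. Section 8.3.4 forces a new count whenever the screening result is more than 3 days old, and the investigator must review it. Its eligibility sentence comes straight after and can be read as testing that result. Criterion 5 can also be read as demanding adequate unsupported counts, because the no-support condition qualifies the limits listed under it. The investigator confirms eligibility (Section 8.1) and the sponsor reviews it (Section 5). Most of this stands: a low count would be seen, and a careful site would probably act on it. What does not follow is that the protocol tells the site the participant is then ineligible.

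A reader might go further and infer that the Phase 1b DLT rate is biased upward. The documents do not support that. Section 4.3.4 excludes events reasonably attributed to the disease or to preexisting conditions, and where the baseline is already abnormal it requires a shift judged clinically significant. All six hematologic limbs in Section 4.3.4.1 exclude events that the disease explains. SAP Section 3.4 takes the last pre-treatment value as safety baseline, so the low count would be on record. Section 6.9.4 lets the dose level review team declare a participant who needs transfusion or growth factor non-evaluable. These filters depend on judgment, and Section 6.9.4 equally allows the team to call a DLT, so they reduce the risk without removing it.

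The Table 12 shifts follow from any additional DLT in a small cohort and do not measure this gap.

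**Conclusion.** The anchor mismatch is real. As written, a supported count from half of the screening window can satisfy criterion 5, and it is unclear whether the fresh pre-C1D1 count must meet the same limits. The gap is at least platelets from 50,000 up to 90,000/µL and at most all three counts, depending on whether Section 6.6.2 covers Cycle 1. It could admit participants without the unsupported marrow function that Section 2.3.1 relies on, and could add hematologic events in cohorts of 2 to 4.

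The 14-of-28-day figure is a calendar span. It says nothing about how often supported counts were used, and the documents give no such frequency. One affected participant alters a dose decision only through a DLT that passes the Section 4.3.4 filters and would not otherwise have occurred. Because Phase 2 will not be initiated, the point bears on interpreting Phase 1b and on any reuse of this text.

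**What to change.** Anchor the change at Section 5.1, criterion 5, and reconcile it with the Table 1 screening window and Sections 6.6.2, 6.9.4 and 8.3.4. The existing washout and the existing count limits should refer to the same sample, and the text should state whether the already scheduled pre-C1D1 count must meet criterion 5. Section 8.3.4 should say which sample its single-repeat sentence means, and Section 6.6.2 should say whether it applies to Cycle 1. This takes about a sentence in each place, with no new limit and no extra blood draw. The cost is an occasional late screen failure.

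For participants already enrolled, list for each DLT-evaluable participant the date of the qualifying sample, the date of the last transfusion or growth factor before C1D1, and the pre-C1D1 ANC, platelet and hemoglobin values. The listing would show whether the gap was ever used and whether any hematologic DLT occurred in such a participant.

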#### **8.3.4.1. Alternative Facilities for Clinical Safety Laboratory Assessment**

Protocol-specified safety laboratory evaluations (refer to [SoA](#)) may be conducted at a local laboratory, during a mobile visit, or at home if permitted by local regulations. The local laboratory may be a standalone institution or within a hospital.

If a local laboratory is used, qualified study site personnel must order, receive, and review results. Site staff must collect the local laboratory reference ranges and certifications/accreditations for filing at the site. Laboratory test results are to be provided to the site staff as soon as possible. The local laboratory reports should be filed in the participant's source documents/medical records. Relevant data from the local laboratory report should be recorded on the CRF.

#### **8.3.5. Pregnancy Testing**

Pregnancy tests will be performed in WOCBP at the times listed in the [SoA](#). A serum pregnancy test is required at Screening. Following screening, pregnancy tests may be urine or serum tests, and must have a sensitivity of at least 25 mIU/mL  $\beta$ -HCG. Following a negative pregnancy test result at Screening, appropriate contraception must be commenced and a second negative pregnancy test result will be required at the baseline visit prior to the participant's receiving the study treatment. Pregnancy tests will also be done whenever 1 menstrual cycle is missed during the active treatment period (or when potential pregnancy is otherwise suspected) and at the end of the study. Additional pregnancy tests must be performed per the local lenalidomide label.

Pregnancy tests may also be repeated if requested by IRBs/ECs or if required by local regulations. If a urine test cannot be confirmed as negative (eg, an ambiguous result), a serum pregnancy test is required. In such cases, the participant must be excluded if the serum pregnancy result is positive.

Consult also the lenalidomide PPP ([Section 10.4.5](#)).

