### 4.2.3. Choice of Contraception/Barrier Requirements

There are no data on the use of tafasitamab in pregnant women. However, IgG is known to cross the placenta and tafasitamab may cause fetal B-cell depletion based on pharmacological properties.

Studies to evaluate the developmental toxicity of PF-07901801 have not been conducted.

Lenalidomide is known to cause risk for severe manifestations of developmental toxicity in humans. Therefore, the use of a highly effective method of contraception is required (see [Appendix 4](#)). The conditions of the PPP for lenalidomide that have been set by the manufacturer ([Section 10.4.5](#)) must be fulfilled for all participants unless there is reliable evidence that the participant does not have childbearing potential. Refer also to the local prescribing information for contraception guidelines for lenalidomide.

The duration of the contraception required after the last dose of study intervention is 4 weeks for male participants and 90 days for female participants; and contraception should be initiated 4 weeks before the start of study intervention (see [Appendix 4](#) for details).

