### 10.4.2. Female Participant Reproductive Inclusion Criteria

The criteria below are part of Inclusion Criterion No. 1 (Age and Sex; [Section 5.1](#)) and specify the reproductive requirements for including female participants. Refer to [Section 10.4.4](#) for a complete list of contraceptive methods permitted in the study.

A female participant is eligible to participate if she (a) is not pregnant or breastfeeding; and (b) agrees not to donate eggs (ova, oocytes) for the purpose of reproduction from the time of screening through 90 days after the last dose of study intervention; and (c) at least 1 of the following conditions applies:

- Is not a WOCBP (see definition in [Section 10.4.3](#)).

OR

- Is a WOCBP and agrees to use a contraceptive method that is highly effective (failure rate of <1% per year) with low user dependency during the intervention period and agrees to use it for at least 90 days after the last dose of study intervention, which corresponds to the time needed to eliminate any reproductive safety risk of the study intervention(s). The investigator should evaluate the effectiveness of the contraceptive method in relationship to the first dose of study intervention.

OR

- Is a WOCBP and agrees to use a highly effective (failure rate of <1% per year) user-dependent method of contraception during the intervention period and for at least 90 days after the last dose of study intervention, which corresponds to the time needed to eliminate any reproductive safety risk of the study intervention(s). In addition to her use of the highly effective method above, she agrees to concurrently use an effective barrier method. The investigator should evaluate the effectiveness of the contraceptive method in relationship to the first dose of study intervention.

In the event that a WOCBP participant has discontinued 2 of the 3 combination therapies and remains on monotherapy: the contraceptive method must be used for at least 45 days after the last dose of PF-07901801 monotherapy, for at least 28 days after the last dose of lenalidomide monotherapy and/or for at least 90 days after the last dose of tafasitamab.

The investigator is responsible for review of medical history, menstrual history, and recent sexual activity to decrease the risk for inclusion of a woman with an early undetected pregnancy. This is to be documented in the source documentation.

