**Steps the Healthcare Professional must follow for this protocol:**

[figure not shown]
1. Receive Healthcare Professional/Prescriber PPP educational materials (as supplied by the Sponsor and specific by region);
2. Inform the participant regarding the benefits and risks of treatment with lenalidomide, not sharing lenalidomide, not donating blood, risks associated with fetal exposure, and the necessity to take adequate measures to avoid fetal exposure to lenalidomide;
3. Give the participant the appropriate corresponding educational brochure (for participants of childbearing potential, for participants not of childbearing potential, or for male participants) and counsel the participant on contraception requirements and emergency contraception use (in countries where available);
4. Apply steps from the PPP algorithm (see [Figure 4](#)). The Healthcare Professional must evaluate the participant from a reproductive potential point of view prior to the start of the study and every 4 weeks prior to dispensing lenalidomide, to ensure that:
  - Male participants are informed that they must use condoms if engaging in sexual intercourse with pregnant women or women of childbearing potential (even if the participant had a vasectomy) and must not donate sperm during lenalidomide treatment and for **4 weeks after cessation of lenalidomide**.
  - Female participants must meet one of the following conditions to be considered of non-childbearing potential:
    - Aged 50+ and naturally occurring amenorrhea of over 1 year (amenorrhea that occurred as a result of cytostatic therapy or during breastfeeding period does not exclude the possibility that the participant is fertile);
    - Premature ovarian failure that was confirmed by a gynecologist;
    - Bilateral salpingo-oophorectomy or hysterectomy as part of medical history;
    - XY genotype, Turner syndrome, uterine agenesis.
  - Female participants of childbearing potential must be informed of the necessity to:
    - Utilize highly effective contraceptive method(s) as per the PPP or other applicable program for 4 weeks before treatment, during treatment, and for 90 days after complete cessation of treatment [4 weeks after cessation is the standard timing for lenalidomide but note that a longer duration is required per

SmPC for MINJUVI (tafasitamab)], including during temporary discontinuation of treatment; or

- To maintain total and continuous abstinence; and

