- To take, under medical supervision, pregnancy tests with a sensitivity of at least 25 mIU/mL, after utilizing an efficient contraceptive measure for at least 4 weeks, every 4 weeks (including during temporary discontinuation of treatment), at EOT, and 4 weeks after lenalidomide discontinuation. This also includes women of childbearing potential who practice total and continuous abstinence.
- During treatment before lenalidomide is dispensed:
  - For female participants of childbearing potential, counsel the participant on contraception requirements and emergency contraception use (in countries where available) and ensure that the required pregnancy test is negative.
  - For male participants, counsel the participant on the barrier contraception requirements and emergency contraception use (in countries where available).
- Do not dispense more than a 28-day supply of lenalidomide.

Follow instructions in the PPP educational materials if a pregnancy occurs.

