#### **Required Contraception Period**

Japanese participants must initiate use of contraceptive method at least 28 days prior to the first dose of the study drug.

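### Section 8.3.5 starts contraception after a Screening test taken at most 28 days before first dose, while 4.2.3, 10.4.5 and 10.10.2 call for 4 weeks of it before study drug: the timings fit together on one day only

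*Protocol*

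**What the plan says.** All of these passages are in the current protocol.

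- **Section 8.3.5 (Pregnancy Testing):** "Following a negative pregnancy test result at Screening, appropriate contraception must be commenced"; then "a second negative pregnancy test result will be required at the baseline visit prior to the participant's receiving the study treatment". It gives no minimum interval between starting contraception and first dose. It ends by referring the reader to the PPP in 10.4.5.
- **Table 1 (Schedule of Activities):** "All screening should be done ≤28 days before the first dose, unless noted otherwise". Section 5.4 describes the same window, Day -28 to Day -1, when it covers re-use of screening samples.
- **Section 4.2.3:** "contraception should be initiated 4 weeks before the start of study intervention".
- **Section 10.4.5 (PPP):** women of childbearing potential are to be told of the need to do the following: "Utilize highly effective contraceptive method(s) as per the PPP or other applicable program for 4 weeks before treatment". Total and continuous abstinence is the alternative. Pregnancy tests are to be taken "after utilizing an efficient contraceptive measure for at least 4 weeks".
- **Section 10.10.2 (Japan):** "Japanese participants must initiate use of contraceptive method at least 28 days prior to the first dose of the study drug".
- **Section 10.4.2 (female inclusion criteria):** contraception is to be used "during the intervention period and agrees to use it for at least 90 days after the last dose of study intervention". No period before treatment is stated, although the investigator is asked to evaluate the method's effectiveness in relation to first dose.
- **Appendix 4, opening paragraph:** says the PPP details are in 10.4.2. They are in 10.4.5.

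**The concern.** Section 8.3.5 is where a site looks for the order of pregnancy test, contraception and first dose. Its order makes the Screening test the trigger for contraception, and Screening cannot be earlier than 28 days before dosing. The other sections ask for 28 days of contraception before dosing. The trigger therefore comes too late for the lead-in on every screening day but one.

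The risk assessment in 2.3.1 says a human teratogenic effect of lenalidomide is to be expected, and 4.2.3 makes the PPP conditions compulsory unless there is reliable evidence of no childbearing potential. A site that follows the sequence literally could miss a compulsory safety condition without noticing. The likely result is a protocol deviation. The worst result is fetal exposure.

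**Working it through.** The plan gives no figure to reproduce. The check is a day count.

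**Inputs**
- Required lead-in: 4 weeks = 4 × 7 = 28 days (4.2.3 and 10.4.5; 10.10.2 states 28 days directly).
- Day of the Screening test: Day -k, with k from 1 to 28 (Table 1; 5.4).
- Days from the test to the start of contraception: d ≥ 0, because 8.3.5 places the start after a negative result.
- First lenalidomide dose: C1D1 (6.1.1.3), so first dose of study intervention and first dose of lenalidomide coincide.

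**Formula**
Lead-in available = k − d. The condition is k − d ≥ 28. Since k ≤ 28 and d ≥ 0, it holds only for k = 28 and d = 0.

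**Results**

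| Screening test | Start of contraception | Lead-in (days) | Shortfall (days) |
|---|---|---|---|
| Day -28 | same day | 28 | 0 |
| Day -28 | 1 day later | 27 | 1 |
| Day -21 | same day | 21 | 7 |
| Day -14 | same day | 14 | 14 |
| Day -7 | same day | 7 | 21 |

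With a same-day start, 1 of the 28 possible screening days meets the lead-in. With a start one or more days after the test, none does.

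**Does another passage relieve the conflict?**
- Table 1 allows exceptions to the 28-day limit where they are noted. Section 8.2 makes one for imaging (up to 42 days before dosing). I found none for contraception or for the Screening pregnancy test.
- The contraception check row in Table 1 covers Screening and C1D1 and refers to 4.2.3 and Appendix 4. It states no required duration itself.
- A reader who goes to Appendix 4 for the PPP is directed to 10.4.2, the section without a lead-in.

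The test timing in 10.4.5 is not a separate problem. If a woman has had 4 weeks of contraception before dosing, a baseline test just before dosing falls after those 4 weeks. It fails only where the lead-in has already failed.

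**The case against.** The strongest reply is that the PPP governs. Section 4.2.3 makes its conditions compulsory, 10.4.5 applies them on top of other protocol requirements, inclusion criterion 1 cites 10.4.5 alongside 10.4.2, and 8.3.5 itself points to the PPP. Most of this stands, and it rules out three stronger readings:

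- **That the protocol lets women receive lenalidomide without the lead-in.** It does not. Such dosing would breach 10.4.5.
- **That the inclusion criterion admits a woman who started contraception a few days before C1D1.** Section 10.4.2 alone states no lead-in, but it is only part of criterion 1, which also brings in the PPP.
- **That a site following 10.4.5 cannot finish screening in the window, or that one following the schedule is bound to breach the PPP.** Nothing bars contraception begun before Screening, and women already using it or abstinent can satisfy every passage. Day -28 also works, and the schedule's contraception check leads to 4.2.3.

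The reply settles which obligation binds. It does not make the 8.3.5 order workable for a woman who first starts contraception after the Screening test. Because the PPP binds, the 8.3.5 sequence is the text that leads a site towards a deviation.

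Two further points count against the concern. Figure 4, the PPP algorithm, cannot be read in the copy reviewed and may give more detail, as may the regional PPP materials. And the study is being terminated: Phase 2 will not start, and Phase 1b was planned for about 20 participants.

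**Conclusion.** The inconsistency is real and should be corrected. For a woman neither using contraception nor abstinent at Screening, 8.3.5 and the 28-day window meet the 4-week lead-in only with test, result and start all on Day -28. Otherwise the shortfall is at least 1 day, and 14 or 21 days for a test on Day -14 or Day -7.

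This is a conflict in stated timing that a site could misapply. It is not a gap through which the protocol authorises dosing.

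The conclusion assumes that 4 weeks means 28 days, that contraception starts no earlier than the Screening test, and that no exception for contraception is noted in material that cannot be seen. The documents do not say how many enrolled women were of childbearing potential. The number affected is probably small, and prospective impact is limited by the termination.

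**What to change.** Reconcile 8.3.5, 10.4.2 and the 28-day Screening window with 4.2.3, 10.4.5 and 10.10.2, so that the protocol states one consistent pre-treatment contraception timing that can be achieved. Which timing that is, and how it fits with Screening, is for the sponsor to decide. Correct the opening paragraph of Appendix 4 so that it points to 10.4.5 for the PPP. The Figure 4 footnote has the reverse error, citing 10.4.5 for monotherapy details that are in 10.4.2, and can be corrected at the same time.

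For women already treated, the sponsor can check whether the lead-in was met and report any failure with the potentially important protocol deviations (SAP 6.6.2.2).

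The cost is wording in a few sections and possibly a later first dose for the few women affected. No analysis changes.
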